### 9.3.1 General Analysis Considerations

Continuous variables (e.g., age) will be summarized using the minimum, 25th, 50th (median), 75th, and maximum values along with the mean and standard deviation, as appropriate. Generally, rank based nonparametric tests will be used to compare continuous variables among patient subgroups. Categorical variables (e.g., objective response) will be summarized in frequency tables and compared among patient subgroups using the chi-square test. Linear regression and logistic (or ordinal logistic) regression will be used to construct multivariable models for continuous, binary, and ordinal variables, as appropriate. In addition to ORR, the distributions of progression-free and overall survival will be estimated using the Kaplan-Meier method. We will consider statistical comparisons statistically, but not necessarily clinically, significant for  $p<0.05$ .

Dose limiting toxicity (see [Section 5.2.4](#)) will be monitored in this phase II clinical trial using a Bayesian approach. A maximum of 34 patients will be enrolled and toxicity monitoring will begin when the 6th patient is evaluable for toxicity. It is expected that the toxicity rate is maintained at approximately 20% (maximum probability of DLT of 0.2, prior distribution (1,1), cohort size 1, and posterior probability  $> 80\%$ ). Pursuant to this rule, patients will be monitored according to the stopping boundaries outlined in [Table 10](#). For example, the protocol will pause for review due to excessive toxicity if 2 or more DLTs are experienced by the first 6 patients treated. 9 DLTs will be allowed among 34 patients treated.

### 9.3.2 Adverse Events

Adverse Events (AEs) will be coded using the MedDRA dictionary and displayed in tables and listings using System/Organ/Class (SOC) and Preferred Term.

Number of DLTs	Of total number of patients treated
2	6
3	10
4	14
5	19
6	23
7	27
8	31
9	34

**Table 10.** Toxicity stopping rules. The expansion phase will be paused for review if DLT rate exceeds above.

Analyses of AEs will be performed for those events that are considered to be treatment emergent AEs (TEAEs), defined as any AE with onset or worsening of a pre-existing condition on or after the first administration of study medication through 28 days following last dose or any event considered drug-related by the investigator through the end of the study. AEs with partial dates will be assessed using the available date information to determine if treatment-emergent; AEs with completely missing dates will be assumed to be treatment-emergent.

AEs will be summarized by patient incidence rates. In all tabulations, a patient may contribute only once to the count for a given AE preferred term.

The number and percentage of patients with TEAEs will be summarized, as well as the number and percentage of patients with TEAEs assessed by the Investigator as at least possibly related to treatment. The number and percentage of patients with any Grade  $\geq 3$  TEAE will be tabulated in the same manner. In the event a patient experiences repeated episodes of the same TEAE, the event with the highest severity and/or strongest causal relationship to study treatment will be used for purposes of tabulations. Serious AEs (SAEs) will also be tabulated.

No formal hypothesis-testing analysis of AE incidence rates will be performed.

All AEs (treatment emergent and post-treatment) will be listed in patient data listings. Separate by-patient listings will be provided for the following: patient deaths, SAEs, and AEs leading to withdrawal.

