**Statistical Analysis:**

Assuming a historical ORR of 15%, per the phase II efficacy trial, Simon's optimal two-stage design calls for a total of 34 patients. A preliminary efficacy assessment will be performed following enrollment of the first 20 patients. If  $\geq 3/20$  enrolled patients achieve a CR, this is sufficient to continue enrollment for the remainder of the study. If  $\geq 9/34$  patients respond, we will reject ( $p < 0.05$ ) the null hypothesis that the true response rate of the regimen is less than or equal to 15%. If the true response rate is 35% or greater, this study design has 80% probability of rejecting the null hypothesis. If the true response rate is low at 15%, the probability of early termination is 60% with an expected sample size of 19 patients.

Toxicity will be monitored in the expansion phase using a Bayesian approach. Toxicity monitoring will begin when the 6th patient is evaluable for toxicity. It is expected that the toxicity rate is maintained at approximately 20% (maximum probability of DLT of 0.2, prior distribution (1,1), cohort size 1, and posterior probability  $> 80\%$ ). Enrollment will be paused if toxicity exceeds this rate.

The maximum number of patients enrolled (n=51) reflects an anticipated drop out of 15% (n=5) and enrollment of 6-12 additional patients if dose level 0 is deemed toxic.

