**Pre-remission phase:**

Dose Level 1:      DEC-C 100mg/35mg on days 1-5  
                         Venetoclax 400mg/day x 28 days

Dose Level -1:      DEC-C 100mg/35mg on days 1-4  
                         Venetoclax 400mg/day x 28 days

Dose Level -2:      DEC-C 100mg/35mg on days 1-4  
                         Venetoclax 400mg/day x 21/28 days

Three initial patients will be enrolled at dose level 1 during the pre-remission phase of treatment. If there are 0 dose limiting toxicities (DLTs), then enrollment will proceed at this dose level. If there is 1 DLT, then 3 additional subjects will be enrolled. If  $\geq 2$  DLTs in six patients, dose level -1 will be evaluated using a similar approach, followed by dose level -2. See [Table 4](#).

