**Table 4: Dose De-escalation Rules**

Number of Patients with Drug-Related DLT at a Given Dose Level	Dose De-escalation Step
0 of 3	Proceed as RP2D
1 of 3	Treat 3 more patients at the same dose level
$\geq 2$ of 3	Enrollment at this dose level stops. Proceed to next lower dose level
$\leq 1$ of 6	Proceed as RP2D
$\geq 2$ of 6	Proceed to next lower dose level

All patients will be considered evaluable for DLT unless they cannot complete the first cycle of therapy due to withdrawal of consent or disease progression. A patient who is not DLT-evaluable will be replaced. Cohort review discussions will be held between the study chair and other investigator(s) to confirm dose escalation, reductions, and cohort expansions.

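### The Table 10 caption pauses only above the tabled DLT counts, but the stated posterior rule and the worked example pause at those counts, and the sentence on 9 of 34 conflicts in the same way

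*Combined protocol and SAP*

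**What the plan says.** Section 9.3.1 sets the DLT monitoring rule: a limit on the DLT rate ("maximum probability of DLT of 0.2"), a (1,1) prior, review after each patient from the 6th evaluable patient, at most 34 patients, and a pause when the posterior probability is above 80%. It presents Table 10 as the boundaries that follow from this rule: 2/6, 3/10, 4/14, 5/19, 6/23, 7/27, 8/31 and 9/34 (DLTs/patients treated).

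Three statements then say how to use the table:

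- The worked example in Section 9.3.1: "the protocol will pause for review due to excessive toxicity if 2 or more DLTs are experienced by the first 6 patients treated".
- The sentence that follows it: "9 DLTs will be allowed among 34 patients treated".
- The Table 10 caption in Section 9.3.2: "The expansion phase will be paused for review if DLT rate exceeds above".

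The plan also describes the monitored patients in two ways. The synopsis says "Toxicity will be monitored in the expansion phase using a Bayesian approach", while Section 9.3.1 says DLTs "will be monitored in this phase II clinical trial using a Bayesian approach". The first patients are separately governed by Section 5.2.2 and Table 4. After three patients, "If there is 1 DLT, then 3 additional subjects will be enrolled". At two or more of three, Table 4 says "Enrollment at this dose level stops. Proceed to next lower dose level", and two or more of six also leads to the next lower level.

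**The concern.** At exactly the tabled count the plan gives opposite instructions. With 2 DLTs in 6 patients the example pauses and the caption continues, because 2/6 does not exceed 2/6. The 9/34 sentence treats the last boundary as tolerated, while the example treats the first as a pause point, so the two ends of one table follow different conventions.

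This is a safety threshold, and someone monitoring DLTs is likely to work from the table and its caption. That reader would continue at counts the stated rule flags, and the result is a missed or later pause for review. The size of the loss also depends on whether the Table 4 patients are among those counted, which the plan does not settle.

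**Working it through.** **Inputs.** DLT limit 0.2, Beta(1,1) prior, cohort size 1, posterior limit 0.80, first look at patient 6 and maximum 34 (Section 9.3.1); boundaries from Table 10; de-escalation rules from Table 4.

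**Step 1: reproduce Table 10.** With x DLTs in n patients the posterior is Beta(1+x, 1+n−x), so

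P(rate > 0.2) = 1 − BetaCDF(0.2; 1+x, 1+n−x) = P(Bin(n+1, 0.2) ≤ x).

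For 2/6 this is P(Bin(7, 0.2) ≤ 2) = 0.2097 + 0.3670 + 0.2753 = 0.852. For all rows:

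| Table 10 row | At the tabled count | One DLT fewer | One DLT more |
|---|---|---|---|
| 2/6 | 0.852 | 0.577 | 0.967 |
| 3/10 | 0.839 | 0.617 | 0.950 |
| 4/14 | 0.836 | 0.648 | 0.939 |
| 5/19 | 0.804 | 0.630 | 0.913 |
| 6/23 | 0.811 | 0.656 | 0.911 |
| 7/27 | 0.818 | 0.678 | 0.910 |
| 8/31 | 0.825 | 0.698 | 0.910 |
| 9/34 | 0.854 | 0.745 | 0.925 |

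Every tabled count crosses 0.80 and no count one lower does. Applying each row to all n up to its tabled n, the smallest count that crosses equals the Table 10 count at all 29 looks from patient 6 to 34. The table therefore matches the rule exactly when read as at or above. Under that rule the most DLTs in 34 patients without a pause is 8 (0.745), not 9 (0.854).

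**Step 2: size if Table 10 covers only patients not governed by Table 4.** This is an exact recursion over binomial paths, with independent DLTs, a constant true rate and a look after each patient from the 6th. The caption can be read as a count (one more DLT than tabled) or as a rate compared with the next or the previous row, so three versions are shown.

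| Probability of a pause | True rate 0.20 | 0.30 | 0.40 |
|---|---|---|---|
| Patient 6, at or above | 0.345 | 0.580 | 0.767 |
| Patient 6, caption (any reading) | 0.099 | 0.256 | 0.456 |
| By patient 34, at or above | 0.570 | 0.898 | 0.990 |
| By patient 34, caption as count | 0.308 | 0.754 | 0.964 |
| By patient 34, caption as rate, next row | 0.484 | 0.861 | 0.984 |
| By patient 34, caption as rate, previous row | 0.441 | 0.844 | 0.982 |

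**Step 3: size if the first six are also the Table 4 patients.** Table 4 acts at 2 or more of 3, or at 1 of 3 followed by 2 or more of 6. Of the 15 orderings of exactly 2 DLTs in 6, only those with 0 of 3 and then 2 of the next 3 escape it, which is 3 of 15. The gap between the two readings at patient 6 is therefore

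(1−p)³ × 3p²(1−p) = 3p²(1−p)⁴ = 0.049, 0.065 and 0.062 at p = 0.20, 0.30 and 0.40.

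| Table 4 action or pause | 0.20 | 0.30 | 0.40 |
|---|---|---|---|
| By patient 6, at or above | 0.345 | 0.580 | 0.767 |
| By patient 6, caption | 0.296 | 0.515 | 0.705 |
| By patient 34, at or above | 0.570 | 0.898 | 0.990 |
| By patient 34, caption as count | 0.419 | 0.803 | 0.972 |
| By patient 34, caption as rate, next row | 0.536 | 0.878 | 0.986 |
| By patient 34, caption as rate, previous row | 0.505 | 0.865 | 0.984 |

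**Step 4: the 9/34 sentence alone.** Keeping at or above but tolerating 9 DLTs at patients 32 to 34 changes the pause probability by patient 34 from 0.570 to 0.566, 0.898 to 0.891 and 0.990 to 0.988.

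**The case against.** The best defence is that the intent can be recovered. Section 9.3.1 gives the full posterior rule, ties Table 10 to it and gives an example that pauses at the tabled count; the arithmetic confirms at or above. On that view this is loose wording in one caption and one sentence. It is true that a careful reader can rebuild the rule. But two of the statements about how to use the table point the other way, and a reader of the table and caption alone would apply them.

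Several points on size stand. The caption speaks of a rate, and on the rate readings the loss by patient 34 in Step 2 is only 4 to 5 points at a true rate of 0.30 and under one point at 0.40. The gap at patient 6 does not shrink on those readings. A true rate of 0.20 equals the stated maximum, so fewer pauses there are mostly fewer false pauses; only the 0.30 and 0.40 columns bear on a missed signal. If the same six patients fall under Table 4, most of the early gap closes. The 9/34 sentence is practically immaterial on its own.

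The action is also a pause for review, not termination. DLTs are reported within one business day (Section 5.2.4), and the data and safety monitoring committee reviews serious adverse events quarterly and meets ad hoc (Section 10.6.6). These limit the harm, but neither supplies a numerical boundary that would resolve the conflict.

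**Conclusion.** The concern holds. Table 10 is numerically correct for the stated rule. Its caption and the 9/34 sentence contradict that rule and the worked example, and nothing else in the plan resolves this.

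At a true DLT rate of 0.30, following the caption lowers the chance of a pause at patient 6 from 58% to 26% if Table 4 does not cover those patients. If it covers the same six, the chance of an action or pause falls from 58.0% to 51.5%. By patient 34, 90% falls to 75–86% in the first case and to 80–88% in the second, depending on how the caption is read. These figures assume independent DLTs at a constant rate and a look after each patient from the 6th. The contradiction itself does not depend on those assumptions. It should be corrected, although other safeguards reduce its consequence.

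**What to change.** Reconcile the caption and the 9/34 sentence with the posterior rule and the worked example, so that one inequality applies to every row. If the 80% posterior limit stands, the caption should say that the phase pauses when the number of DLTs is equal to or greater than the number shown, and 9 of 34 should be described as a pause point. If a looser boundary is intended, restate the posterior limit and regenerate Table 10 and the example from it.

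In the same edit, state in the synopsis and Section 9.3.1 whether patients evaluated under Table 4 count towards the Table 10 totals.

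The cost is the wording of one caption and a few sentences, with no cost to patients or budget.

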### **9.3.3 Laboratory Data**

The actual value and change from baseline for each on study evaluation will be summarized for each clinical laboratory parameter, including hematology and clinical chemistry, by arm, and for all study patients combined. In the event of repeat values, the last non-missing value per study day/time will be used.

Severity of select clinical lab measures will be determined using CTCAE criteria (e.g., those measures that have a corresponding CTCAE grade classification). Labs with CTCAE Grades  $\geq 3$  will be presented in a data listing. Shift tables that present changes from baseline to worst on-study values relative to CTCAE classification ranges will be produced.

### **9.3.4 Vital Signs and Physical Examinations**

The actual value and change from baseline to each on-study evaluation will be summarized for vital signs for all study patients combined. By-patient listings of vital sign measurements will be presented in data listings.

Physical examination results at screening will be summarized; all other abnormal physical examination data will be recorded. All examination findings will be presented in a data listing.

## 10 REGULATORY AND ETHICAL COMPLIANCE

### 10.1 Protocol Review and Amendments

Information regarding study conduct and progress will be reported to IRB per current institutional standards.

The trial will not be initiated until there is approval by the local IRB of the protocol, informed consent document and any other material used to inform the patient about the nature of the trial. The IRB should be duly constituted according to local regulatory requirements. The investigator will inform the IRB of the progress of the trial at least yearly.

Any changes to the protocol will be made in the form of a written amendment and must be approved by the study chair and the local IRB prior to local implementation. All amendments will also be submitted as necessary to the FDA by the study chair (or designee).

Protocol changes to eliminate an immediate hazard to a trial patient may be implemented by the investigator immediately. The investigator must then immediately inform the local IRB; and the study chair (or designee), who will communicate as appropriate with the FDA.

The study chair (or designee) is responsible for the coordination and development of all protocol amendments, and will disseminate this information to the participating centers.

### 10.2 Informed Consent

The investigator (or his/her designee) will explain to each subject the nature of the study, its purpose, the procedures involved, the expected duration, the potential risks and benefits involved and any discomfort it may entail. Each subject will be informed that participation in the study is voluntary, that s/he may withdraw from the study at any time, and that withdrawal of consent will not affect subsequent medical treatment or relationship with the treating physician(s) or institution. The informed consent will be given by means of a standard written statement, written in non-technical language, which will be IRB approved. The subject should read and consider the statement before signing and dating it, and will be given a copy of the document. No subject will enter the study or have study-specific procedures done before his/her informed consent has been obtained.

In accordance with the Health Information Portability and Accountability Act (HIPAA), the written informed consent form (or a separate document to be given in conjunction with the consent document) will include a subject authorization to release medical information to the study sponsor and supporting agencies and/or allow these bodies, a regulatory authority, or Institutional Review Board access to subjects' medical information that includes all hospital records relevant to the study, including subjects' medical history.

### 10.3 Ethics and Good Clinical Practice

This study will be carried out in compliance with the protocol and Good Clinical Practice (GCP), as described within:

1. ICH Harmonized Tripartite Guidelines for Good Clinical Practice 199639
2. US 21 Code of Federal Regulations dealing with clinical studies (including parts 50 and 56 concerning informed consent and IRB regulations).
3. Declaration of Helsinki, concerning medical research in humans (Recommendations Guiding Physicians in Biomedical Research Involving Human Subjects, Helsinki 1964, amended Tokyo 1975, Venice 1983, Hong Kong 1989, Somerset West 1996).

The investigator agrees to adhere to the instructions and procedures described within the above and thereby to adhere to the principles of Good Clinical Practice with which the above conform.

### 10.4 Confidentiality

It is the responsibility of the investigator to ensure that the confidentiality of all patients participating in the trial and all of their medical information is maintained. Case report forms and other documents submitted to regulatory authorities must not contain the name of a trial patient. All patients in the trial will be identified by a unique identifier, which will be used on all CRFs and any other material submitted to regulatory authorities. All case report forms and any identifying information must be kept in a secure location with access limited to the study staff directly assisting with the trial.

### 10.5 Study Termination

The study chair reserves the right to terminate the study at any site and at any time. Reasons for study termination may include, but are not limited to, the following:

- Investigator non-compliance with the protocol, GCP or regulatory requirements
- Insufficient enrollment
- Safety concerns
- Decision by suppliers to modify or discontinue the availability, development or manufacture of DEC-C.
- A request to discontinue the study by the IRB or FDA.

The study chair will promptly notify investigators, the IRB and FDA if the study is terminated for any reason.

### 10.6 Multi-Center Guidelines

#### 10.6.1 Protocol Review and Amendments

Information regarding study conduct and progress will be reported to the IRB per the current institutional standards of each participating center.

Any changes to the protocol will be made in the form of an amendment and must be approved by the IRB of each institution prior to local implementation.

The study chair (or designee) is responsible for the coordination and development of all protocol amendments. Once approved by the study chair, Vanderbilt will disseminate this information to the participating centers.

### **10.6.2 Study Documentation**

Each participating site is responsible for submitting copies of all relevant regulatory documentation to the coordinating center. The required documents include, but are not limited to the following: local IRB approvals (e.g., protocol, consent form, amendments, patient brochures and recruitment material, etc.), IRB membership rosters, summary of unanticipated problems or protocol deviations, and documentation of expertise of the investigators. The coordinating center will provide each participating site with a comprehensive list of the necessary documents. It is the responsibility of the participating sites to maintain copies of all documentation submitted to the coordinating center.

The requirements for data management, submissions, and monitoring are outlined below. The participating sites will submit all the research related information inclusive of:

- Source documents (patient registration list, CRF info, toxicity assessments, tumor measurements / responses, etc.) are required to be provided within 30 days of visit or 10 days in advance of a monitoring visit or audit.
- Essential Documents (IRB approval documents, financial disclosure forms, 1572, delegation of authority log, protocol training, etc.) are required to be provided within one week of receiving the updated documents.

Personnel from the VICC Clinical Trial Shared Resource (CTSR) will monitor the trial and may periodically visit the investigative site to assure proper conduct of the trial and proper collection of the data. The investigators at other sites will allow the monitor to review all source documents used in the preparation of the case reports.

### **10.6.3 Records Retention**

United States (US) FDA regulations (21 CFR §312.62[c]) require that records and documents pertaining to the conduct of this study and the distribution of investigational drug, including CRFs, consent forms, laboratory test results, and medication inventory records, must be retained by each Principal Investigator for 2 years after marketing application approval. If no application is filed, these records must be kept 2 years after the study is discontinued and the US FDA and the applicable national and local health authorities are notified.

Following closure of the study, each participating center will maintain a copy of all site study records in a safe and secure location. The coordinating center will inform the investigator at each site at such time that the records may be destroyed.

#### **10.6.4 Publication**

It is understood that any manuscript or releases resulting from the collaborative research must be approved by the Study Chair and will be circulated to applicable participating sites/investigators prior to submission for publication or presentation.

